#### **Additional analysis**

An overall summary of AESIs including 12-week on-treatment period and 16-week post-treatment follow-up period will be presented.

All AESIs including 12-week on-treatment period and 16-week post-treatment follow-up period will be presented in a listing.

#### **4.3.3. Additional Safety Assessments**

##### **4.3.3.1. Laboratory Data**

Laboratory Data including 12-week on-treatment period and 8-week post-treatment follow-up period will be included in the analysis.

Descriptive statistics for each analyte will be displayed for each week. The tables will display the mean value, standard deviation, median, 25th and 75th percentiles, minimum and maximum. No statistical tests will be performed.

A line graph will be produced for each analyte which displays the mean value by week.

Change from baseline for each analyte will also be summarized for each post-baseline week. The tables will display the mean value, standard deviation, median, 25th and 75th percentiles, minimum and maximum. No statistical tests will be performed.

A line graph will be produced for each analyte which displays the mean change from baseline value by week.

Laboratory toxicity will be graded using Adverse Event Severity Grading Tables when possible. The worst laboratory toxicity grade during treatment for each laboratory parameter within each laboratory category (hematology, liver function, chemistries, urinalysis and immunoglobulins) will be presented.

Toxicity grade shifts from baseline of  $\geq 2$  grades will be summarized during treatment for each laboratory parameter within each laboratory category (hematology, liver function, chemistries, urinalysis and immunoglobulins). The table will display the number and percentage of subjects with at least one  $\geq 2$  grade shift as well as the specific shift categories: Grade 0 to 2, Grade 0 to 3, Grade 0 to 4, Grade 1 to 3, Grade 1 to 4 and Grade 2 to 4.

For laboratory tests without toxicity grades within each laboratory category (hematology, liver function, chemistries, urinalysis and immunoglobulins), shifts relative to the normal range will be summarized for each analyte as shifts 'to low' and shifts 'to high'. For the 'to low category' the percentage of subjects with at least one low post-baseline value, including unscheduled visits, in the study period relative to baseline will be displayed using the categories: no shift to low and normal/high to low. For the 'to high category' the percentage of subjects with at least one high post-baseline value in the study period relative to baseline will be displayed using the categories: no shift to high and normal/low to high. No statistical tests will be performed.

A laboratory value that is above the testing laboratory's normal range will be considered a high abnormal laboratory value. A laboratory value that is below the testing laboratory's normal range will be considered a low abnormal value.

The number and percentage of subjects with immunoglobulin values (IgG, IgA, and IgM) below the LLN at each week will also be presented for all subjects and then repeated for subjects greater or equal to LLN at baseline. No statistical test will be performed.

All clinical laboratory data will be listed.

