1.3. Schedule of Activities (SoA)

1.3.1. Body weight \geq 50 kg, Dose 200 mg QW

Body weight \geq 50 kg, Dose 200 mg QW														
Site Visit	V1	V2	V3	V4	V5, V6	V7	V8-10	V11	V12-13	V14	V15	V16	V17	V18
Procedure	Screening	Treatment Period (12 weeks)											Follow-Up Period ^{1,2}	
Study Day/Week	-35 days	Day 1	Day 4 \pm 1	Day 8 \pm 2	Day 15, 22 \pm 2	Day 29 \pm 2	Day 36, 43, 50 \pm 2	Day 57 \pm 2	Day 64, 71 \pm 2	Day 78 \pm 1	Day 81 \pm 1	Day 85 \pm 2 / EW ¹	8-Week \pm 7-Day Follow-up ¹	16-Week \pm 7-Day Follow-up ^{1,2}
		Wk 0		Wk 1	Wk 2-3	Wk 4	Wk 5-7	Wk 8	Wk 9-10	Wk 11		Wk 12		
Informed consent	X													
Inclusion and exclusion criteria	X													
Demography	X													
Medical history	X													
Safety Assessments														
Concomitant Medication	X	X		X	X	X	X	X	X	X		X	X	
Symptom Driven Physical Exam ³	X	X				X		X				X	X	
Vital Signs	X	X	X	X	X	X	X	X	X	X	X	X	X	
Weight	X	X ⁶		X	X	X	X	X	X	X		X	X	
Height		X				X		X				X	X	
12-Lead ECG	X													

CONFIDENTIAL

217091
Protocol Amendment 2

Body weight ≥50 kg, Dose 200 mg QW														
Site Visit	V1	V2	V3	V4	V5, V6	V7	V8-10	V11	V12-13	V14	V15	V16	V17	V18
Procedure	Screening	Treatment Period (12 weeks)											Follow-Up Period ^{1,2}	
Study Day/Week	-35 days	Day 1	Day 4±1	Day 8±2	Day 15, 22 ±2	Day 29±2	Day 36, 43, 50±2	Day 57±2	Day 64, 71±2	Day 78±1	Day 81±1	Day 85±2 / EW ¹	8-Week±7-Day Follow up ¹	16-Week±7-Day Follow up ^{1,2}
		Wk 0		Wk 1	Wk 2-3	Wk 4	Wk 5-7	Wk 8	Wk 9-10	Wk 11		Wk 12		
Adverse Events		X		X	X	X	X	X	X	X		X	X	X
Serious Adverse Events		X		X	X	X	X	X	X	X		X	X	X
Device Incidents malfunctions		X		X	X	X	X	X	X	X		X		
Laboratory Assessments														
Haematology	X ⁵	X ⁵				X		X				X	X	
Chemistry	X ⁵	X ⁵				X		X				X	X	
Urinalysis	X ⁵	X ⁵				X		X				X	X	
Pregnancy Test ⁴	X ⁵	X ⁵				X		X				X	X	
IgA, IgG and IgM	X	X ⁵				X		X				X	X	
Belimumab Administration and PK Sampling														
PK Sampling	X ⁷	X ⁸	X ¹⁰	X ^{8, 11}						X ⁸	X	X		
Administration of Belimumab		X ⁹		X ⁹	X	X	X	X	X	X				

1.3.2. Body weight ≥ 30 kg - < 50 kg, Dose 200 mg Q10d

Site Visit	V1	V2	V3	V4	V5	V6	V7, V8	V9	V10	V11	V12	V13	V14
Procedure	Screening	Treatment Period (12 weeks)										Follow-Up Period ^{1,2}	
Study Day/Week	-35 days	Day 1	Day 4 \pm 1	Day 11 \pm 2	Day 21 \pm 2	Day 31 \pm 2	Day 41, 51 \pm 2	Day 61 \pm 2	Day 71 \pm 1	Day 74 \pm 1	Day 81 \pm 2 / EW ¹	8-Week \pm 7-Day Follow-up ¹	16-Week \pm 7-Day Follow-up
Informed consent	X												

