- New or worsening symptoms believed to be related to liver injury (such as fatigue, nausea, vomiting, right upper quadrant pain or tenderness, or jaundice) or believed to be related to hypersensitivity (such as fever, rash or eosinophilia)
- Includes: Hepatitis A Immunoglobulin M (IgM) antibody; HBsAg and HBcAb(conduct quantitative Hepatitis B DNA test if positivity for HBsAg and/or HBcAb); hepatitis C RNA; cytomegalovirus IgM antibody; Epstein-Barr viral capsid antigen IgM antibody (or if unavailable, heterophile antibody or monospot testing); and hepatitis E IgM antibody.
- Record the date/time of the PK blood sample draw and the date/time of the last dose of study intervention prior to the PK blood sample draw on the CRF. If the date or time of the last dose is unclear, provide the participant's best approximation. If the date/time of the last dose cannot be approximated OR a PK sample cannot be collected in

the time period indicated above, do not obtain a PK sample. Instructions for sample handling and shipping are in the SRM.

Phase 3/4 liver chemistry increased monitoring criteria with continued therapy

Liver Chemistry Increased Monitoring Criteria – Liver Monitoring Event	
Criteria	Actions

ALT \geq5xULN and $<$8xULN and bilirubin $<$2xULN without symptoms believed to be related to liver injury or hypersensitivity, and who can be monitored weekly for 2 weeks.
 
OR
 
ALT \geq3xULN and $<$5xULN and bilirubin $<$2xULN without symptoms believed to be related to liver injury or hypersensitivity, and who can be monitored weekly for 4 weeks.
	
 • Notify the GSK medical monitor within 24 hours of learning of the abnormality to discuss participant safety. • Participant can continue study intervention • Participant must return weekly for repeat liver chemistries (ALT, AST, alkaline phosphatase, bilirubin) until they resolve, stabilise or return to within Baseline • If at any time participant meets the liver chemistry stopping criteria, proceed as described above • If ALT decreases from ALT \geq5xULN and $<$8xULN to \geq3xULN but $<$5xULN, continue to monitor liver chemistries weekly. • If, after 4 weeks of monitoring, ALT $<$3xULN and bilirubin $<$2xULN, monitor participants twice monthly until liver chemistries normalise or return to within Baseline.

10.7. Appendix 7: Deficiencies: Definition and Procedures for Recording, Evaluating, Follow-up, and Reporting in Medical Device Studies

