#### 4.1.1. General Methodology

Confidence intervals will use 95% confidence levels unless otherwise specified.

Unless otherwise specified, the following will apply:

- Continuous data will be summarized using descriptive statistics: n, mean, standard deviation (std), median, minimum, 25th percentile, 75th percentile and maximum.
- Categorical data will be summarized as the number and percentage of participants in each category.
- Where means or medians are displayed graphically, standard error bars or interquartile ranges (IQRs) will be presented, respectively.
- The minimum and maximum will be reported to the same number of decimal places as the raw data recorded in the database. The mean, median, 25th percentile, and 75th percentile will be reported to one more decimal place than the raw data recorded in the database. The SD will be reported to two more decimal places than the raw data recorded in the database. A maximum of four decimal places will be used. Percentages will be presented to one decimal place. A count of zero will have no corresponding percentage.
- When the data are summarized by week, unscheduled visits will be included.

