### 6.2.3. Assessment Window

Different body weight will have different schedule of visits. Therefore, the data will be analysed by the analysis timepoint (Week 0, Week 2, Week 4, Week 6, Week 8, Week 10, Week 12, 8-week Follow-up and 16-week Follow-up).

Early withdrawal and unscheduled visits will be slotted to the appropriate planned visit. The assigned analysis timepoint will be based on the interval in which the Study Day for the early withdrawal or unscheduled visit falls according to intervals provided below.

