**NOTES:**

- If there are multiple assessments within the same window, a scheduled visit will be prioritized over unscheduled visits. If all assessments within the same window are from unscheduled visits, the earliest one will be taken in the slotting.

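### By-week laboratory means at Weeks 2, 6 and 10 can rest only on unscheduled or early-withdrawal samples, because no safety laboratory test is scheduled at those weeks

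*SAP*

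**What the plan says.** Protocol 1.3 has one schedule per weight cohort. In each, the rows for haematology, chemistry, urinalysis and "IgA, IgG and IgM" are marked at screening, Day 1, three treatment-period visits (about Weeks 4, 8 and 12, the last doubling as the early-withdrawal visit) and the 8-week follow-up. They are blank elsewhere.

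SAP 6.2.3 analyses all data on one grid: "Week 0, Week 2, Week 4, Week 6, Week 8, Week 10, Week 12, 8-week Follow-up and 16-week Follow-up". Its window tables apply to every data domain. It adds: "Early withdrawal and unscheduled visits will be slotted to the appropriate planned visit", with assignment by study day. Within a window a scheduled result takes priority; otherwise, "If all assessments within the same window are from unscheduled visits, the earliest one will be taken in the slotting".

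SAP 4.1.1 sets the general rule: "When the data are summarized by week, unscheduled visits will be included".

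SAP 4.3.3.1 then asks for laboratory output on that grid: "Descriptive statistics for each analyte will be displayed for each week", and "A line graph will be produced for each analyte which displays the mean value by week". Change from baseline gets the same table and graph for each post-baseline week. It also asks for the number and percentage of subjects with immunoglobulins below the lower limit of normal at each week. It does not restrict these outputs to weeks with a scheduled test, and it sets no minimum n for a plotted mean.

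**The concern.** At Weeks 4, 8 and 12 the priority rule protects the summary: a child with a scheduled value contributes that value and no other. At Weeks 2, 6 and 10 there is no scheduled value to take priority, so any result shown there is off-schedule.

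Many off-schedule results are selective. Protocol 8.3.4 requires clinically significant abnormal results to be repeated until they normalise, return to baseline or cease to matter. Protocol Appendix 6 requires weekly liver chemistries once ALT reaches 3 times the upper limit of normal under continued treatment. The early-withdrawal visit repeats the full Week 12 panel.

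A by-week line could therefore run from a near-complete cohort to one or two children and back. With 17 children and no control arm, one child can produce the excursion, and nothing on the graph would show it to be an artefact. SAP 4.1.1 also asks for standard error bars on plotted means, and these are undefined at n=1.

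**Working it through.** The plan states no figure on this point to reproduce. The check is whether any scheduled safety laboratory day can land in a window labelled Week 2, 6 or 10.

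**Step 1: map the scheduled days.** Inputs are the laboratory visit days and their ±2-day windows (Protocol 1.3.1 to 1.3.3) and the analysis windows (SAP 6.2.3).

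| Cohort | Scheduled laboratory days after Day 1 | SAP windows for Weeks 4, 8, 12 | SAP windows for Weeks 2, 6, 10 |
|---|---|---|---|
| ≥50 kg, weekly | 27–31, 55–59, 83–87 | 26–32, 54–60, 83–87 | 12–18, 40–46, 68–74 |
| 30 to <50 kg, every 10 days | 29–33, 59–63, 79–83 | 26–35, 56–65, 78–84 | 8–15, 36–45, 66–72 |
| 15 to <30 kg, every 2 weeks | 27–31, 55–59, 83–87 | 22–35, 50–63, 80–90 | 10–21, 36–49, 64–72 |

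Every scheduled day falls in a Week 4, 8 or 12 window and none in a Week 2, 6 or 10 window. Scheduled contributors at Weeks 2, 6 and 10 are therefore 0 of 17.

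**Step 2: how much of the treatment period those windows cover.** Days run from Day 2 to the end of the Week 12 window.
- Weekly: 7 + 7 + 7 = 21 of 86 days (24%).
- Every 10 days: 8 + 10 + 7 = 25 of 83 days (30%).
- Every 2 weeks: 12 + 14 + 9 = 35 of 89 days (39%).

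These are window lengths, not probabilities. The documents give no rate of unscheduled testing.

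**Step 3: early-withdrawal samples.** With 17 children and the assumed 20% withdrawal rate (SAP 5), 17 × 0.20 = 3.4, so about three children would have an early-withdrawal visit, at study days not known in advance.

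**Step 4: size of a possible excursion (assumed values).** Take an ALT upper limit of normal of 40 U/L, 16 children at 20 U/L, and one child at 160 U/L (4 times the limit) from Week 4 and under weekly monitoring.
- Week 4, all tested: (16 × 20 + 160) / 17 = 480 / 17 = 28.2 U/L, n=17.
- Week 6, only that child tested and unchanged: 160 U/L, n=1.
- Week 8, if that child is back to 20 U/L: (17 × 20) / 17 = 20 U/L, n=17.

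The plotted line rises by a factor of 160 / 28.2 = 5.7 and then falls, although nobody's ALT rose between Weeks 4 and 6.

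**Step 5: the rule acts unevenly across cohorts.** A retest on Day 36 falls in Visit 8 (Days 33–39) in the weekly cohort, which has no week label. In the other two cohorts the same day is Week 6. Which retests reach the grid thus depends partly on weight cohort.

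**The case against.** A reader might infer more than the documents support: that Weeks 2, 6 and 10 will show false excursions, and that every contributor will be a child with a problem. Neither follows.

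- Protocol 8.1.3 allows unscheduled visits for various reasons, and Appendix 2 allows extra tests at any time. A make-up sample could also land in these windows.
- Children may withdraw by their own wish (Protocol 7.1 and 7.2). Their full panel may be normal; it would give an imprecise mean, not necessarily an abnormal one.
- If no off-schedule sample falls in a window, that week is simply empty.
- The ALT illustration is near a worst case. The immunoglobulin counterpart is weaker: the mandatory weekly repeats cover liver chemistries only, and a value just below the lower limit need not be clinically significant. One low repeat would read as 100% below the limit only if the denominator is children tested that week, which the SAP does not state.
- The default statistics in SAP 4.1.1 include n, so the tables would usually expose a mean based on one child. A missing error bar on the graph is itself a hint.
- The analyses are descriptive and the safety endpoint is adverse events. No decision is tied to weekly laboratory means.

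All of this stands, and it limits how likely and how serious the problem is. It does not change the fact that the rules, as written, allow only off-schedule results at Weeks 2, 6 and 10 and ask for them to be plotted beside near-full-cohort means.

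**Conclusion.** The point holds as a defect in the by-week laboratory displays. No haematology, chemistry, urinalysis or immunoglobulin test is scheduled in any Week 2, 6 or 10 window. (PK blood is drawn at some of those visits in the two lower-weight cohorts, but SAP 4.3.3.1 does not summarise it.) Any mean, mean change, graph point or percentage below the lower limit of normal there would rest on a few children who were tested off schedule, often because of an abnormal value or withdrawal.

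The effect depends on at least one such sample falling in windows that cover 24% to 39% of post-Day-1 treatment-period days. How often that will happen cannot be derived from the documents. Weeks 4, 8 and 12 are protected for every child with a scheduled value. The main exposure is the line graphs, for which the SAP asks for no n. The PK results and the adverse-event tables are unaffected. This is worth correcting because it is cheap and the study is small, not because it threatens the study's conclusions.

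**What to change.** Add to SAP 4.3.3.1, as an exception to 4.1.1:

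- By-week laboratory values, changes from baseline, both line graphs and the percentage below the lower limit of normal are limited to timepoints with scheduled laboratory tests: Weeks 0, 4, 8 and 12 and the 8-week follow-up.
- The existing slotting stays for a make-up or early-withdrawal sample that falls in a Week 4, 8 or 12 window when the child has no scheduled value there. A blanket exclusion of off-schedule results would lose these samples, which matters with 17 children.
- All other off-schedule results go into the worst-grade and shift tables, as their study period allows, and into the listing. State this for each table: at present only the shift-to-low rule mentions unscheduled visits.
- Print n under each graph point.

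The cost is a short SAP addition and a filter in the table and graph programs, with no new data. The small downside is that off-schedule results in the Week 2, 6 and 10 windows no longer appear in by-week displays.

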### 4.3. Safety Analyses

The safety analyses will be based on the ITT Analysis Set, unless otherwise specified.

For estimand strategy in safety. The estimand is described by the following attributes:

Population	Chinese paediatric participants 5-17 years of age with systemic lupus erythematosus (SLE) who have previously been treated with IV belimumab
Treatment	
 
Repeat doses of 200mg belimumab administered subcutaneously (SC) over 12 weeks on a background of standard of care therapy
 

Endpoints	
 
Occurrence of adverse events, serious adverse events and adverse events of special interest through Week 12.
 

Summary Measure	
 
Frequency and percentage
 

Intercurrent events and strategies	
 
Discontinuation of study medication, addressed with while-on-treatment strategy. Safety data in the 12-week on-treatment period will be used in analysis.
 

Rationale for Estimand: This attempts to estimate on-treatment safety effects likely to be attributable to the drug.

In addition to estimand strategy in secondary endpoint, an additional analysis will be performed based on all safety data including 12-week on-treatment period and 16-week post-treatment follow-up period.

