## 6.2. Appendix 2 Data Derivations Rule

### 6.2.1. Study Period

Assessments and events will be classified according to the time of occurrence relative to the study intervention period.

Treatment period	Definition
Pre-Treatment	Event start date < IP start date
On-Treatment	IP start date ≤ Event start date ≤ Week 12 Date or Early Withdrawal Date
Post-Treatment	Event start date > Week 12 Date or Early Withdrawal Date

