**Body weight  $\geq$ 50 kg, Dose 200 mg QW**

Analysis Set / Domain	Target	Analysis Window		Analysis Timepoint
		Beginning Timepoint	Ending Timepoint	
All	Day-1	na	na	Screening (Visit 1)
All	Day 1	na	na	Visit 2 (Week 0)
All	Day 4	Day 2	Day 5	Visit 3
All	Day 8	Day 6	Day 11	Visit 4
All	Day15	Day 12	Day 18	Visit 5 (Week 2)
All	Day 22	Day 19	Day 25	Visit 6
All	Day 29	Day 26	Day 32	Visit 7 (Week 4)
All	Day 36	Day 33	Day 39	Visit 8
All	Day 43	Day 40	Day 46	Visit 9 (Week 6)
All	Day 50	Day 47	Day 53	Visit 10
All	Day 57	Day 54	Day 60	Visit 11 (Week 8)
All	Day 64	Day 61	Day 67	Visit 12
All	Day 71	Day 68	Day 74	Visit 13 (Week 10)
All	Day 78	Day 75	Day 79	Visit 14
All	Day 81	Day 80	Day 82	Visit 15
All	Day 85	Day 83	Day 87	Visit 16 (Week 12)
All	Day 141	na	na	Visit 17 (8 week Follow-up)
All	Day 197	na	na	Visit 18 (16 week Follow-up)

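### SAP 4.3.3.1 counts laboratory toxicity grades only during treatment, so a Grade 3–4 value first seen at the 8-week follow-up is counted by grade in no table

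*SAP*

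**What the plan says.** SAP 4.3.3.1 begins with a general inclusion rule: "Laboratory Data including 12-week on-treatment period and 8-week post-treatment follow-up period will be included in the analysis". The two displays that use toxicity grades are then limited. One shows "The worst laboratory toxicity grade during treatment for each laboratory parameter within each laboratory category". The other covers shifts of two or more grades, which "grades will be summarized during treatment for each laboratory parameter within each laboratory category". For tests that have no grading scale the period is worded differently: the low-direction table takes "the percentage of subjects with at least one low post-baseline value, including unscheduled visits, in the study period relative to baseline", and the high-direction table also uses the study period.

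SAP 6.2.1 defines three periods: Pre-Treatment, On-Treatment and Post-Treatment. Post-Treatment is "Event start date > Week 12 Date or Early Withdrawal Date". *During treatment* is not one of the defined terms.

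The protocol's Schedule of Activities (1.3.1 to 1.3.3) draws haematology, chemistry, urinalysis and immunoglobulins at the 8-week follow-up in all three weight tiers.

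Protocol Section 3 and SAP 4.3 both state, after the safety estimand, that "an additional analysis will be performed based on all safety data including 12-week on-treatment period and 16-week post-treatment follow-up period". SAP 4.3.2 and 4.3.2.1 carry this out for AEs and AESIs. SAP 4.3.3.1 has no matching block for laboratory grades. It does say that "All clinical laboratory data will be listed".

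**The concern.** The section admits follow-up laboratory data and then leaves them out of the only two tables that classify laboratory values by severity. It gives no reason. Taken literally, tests that can be graded, such as IgG and neutrophils, get a shorter window than tests that cannot.

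The protocol treats falling IgG as a safety matter. The risk assessment (2.3.1) gives B-cell and IgG reduction as the infection mechanism, and 7.1.2 acts on a Grade 4 IgG. Section 8.3.4 requires clinically significant abnormal values to be repeated when they occur up to 60 days after the last dose. If a child's IgG or neutrophil count first reaches Grade 3 or 4 at the follow-up draw, the count of participants by laboratory grade is incomplete. In a study of about 17 children, one child is 1/17 = 5.9%.

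**Working it through.** The plan gives no figure to reproduce here. The check compares periods and adds some simple arithmetic.

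**1. Does the follow-up draw fall outside On-Treatment?** Draw days and last scheduled dose come from the Schedule of Activities. Target days come from the SAP 6.2.3 window tables.

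| Tier | On-treatment draws (day) | Last scheduled dose | Week 12 target | Follow-up target | Days after Week 12 target | Days after last dose |
|---|---|---|---|---|---|---|
| QW | 29, 57, 85 | 78 | 85 | 141 | 141 − 85 = 56 | 141 − 78 = 63 |
| Q10d | 31, 61, 81 | 71 | 81 | 137 | 137 − 81 = 56 | 137 − 71 = 66 |
| Q2W | 29, 57, 85 | 71 | 85 | 141 | 141 − 85 = 56 | 141 − 71 = 70 |

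It does, in every tier.

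**2. Share of scheduled draws left out of the grade tables.** Three on-treatment draws plus one follow-up draw give 1/4 = 25% in each tier.

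**3. Is drug still present?** Protocol 5.1 ties 16 weeks after the last dose to elimination, with five terminal half-lives as the example. That implies a half-life of 112/5 = 22.4 days. The fraction remaining t days after the last dose is 2^(−t/22.4):

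- QW: 2^(−63/22.4) = 0.142
- Q10d: 2^(−66/22.4) = 0.130
- Q2W: 2^(−70/22.4) = 0.115

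So about 11–14% remains at the SAP target days.

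**4. Where a follow-up value appears in the planned laboratory output.**

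| Display | Period stated | Follow-up value included? | Counted by grade? |
|---|---|---|---|
| By-week statistics and change from baseline, with minimum and maximum | By week, 8-week follow-up a listed timepoint | Yes | No |
| Worst toxicity grade | During treatment | No | – |
| Shift of ≥2 grades | During treatment | No | – |
| Shifts for ungraded tests | Study period | Yes, as worded | No |
| IgG, IgA, IgM below LLN | Each week | Yes | No |
| Listing | All data | Yes | Not a count |

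The LLN table cannot replace a grade count. On the protocol 10.2.1 scale, IgG runs from Grade 1 (550–700 mg/dL) to Grade 4 (below 250 mg/dL), and being below the LLN does not separate these.

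**5. How often would it matter?** The documents give no rate. Assume a proportion p of children have a first Grade 3–4 value at this visit. The chance that at least one of n is missed by the grade tables is 1 − (1 − p)^n:

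| Assumed p | n = 17 | n = 14 |
|---|---|---|
| 1% | 16% | 13% |
| 2% | 29% | 25% |
| 5% | 58% | 51% |
| 10% | 83% | 77% |

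These values of p are illustrative only.

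**The case against.** There is a fair case for the SAP as written.

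- **The commitment may not reach laboratory data.** The all-safety-data sentence is attached to an estimand whose endpoints are AEs, SAEs and AESIs. It refers to a 16-week follow-up, but no laboratory panel other than a home urine pregnancy test is planned at week 16. Protocol 8.3 lists haematology and chemistry only for the 12-week treatment period, and protocol 9.3.3 specifies no laboratory analysis. A reader might infer that the SAP breaks a protocol promise and that its statement of no changes (SAP 4.6) is wrong. The literal words and their place in SAP 4.3 allow that reading but do not establish it.
- **The value is not lost.** With so few participants, an extreme follow-up result would show as the printed minimum or maximum for that visit, and low immunoglobulins are counted against the LLN. Protocol 8.3.4 also requires clinically significant changes to be recorded as AEs, and the AE severity tables have a version covering follow-up. A reader might infer that the report could present the trial as free of Grade 3–4 laboratory toxicity. An unqualified claim of that kind would conflict with these other outputs, while a claim limited to the treatment period would be accurate.
- **On-treatment grading is defensible.** It matches the while-on-treatment strategy. After Week 12 children move to standard of care chosen by the investigator (protocol 6.6), so later changes are harder to attribute to the drug.

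Most of this stands, and it rules out the stronger readings. It does not close the gap. The AE route depends on investigator judgement and uses mild, moderate and severe rather than Grades 1 to 4. None of the other outputs counts participants by grade. The defence of on-treatment tables supports keeping them as primary, not omitting the second period from a section that says follow-up is included.

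**Conclusion.** The point holds as an inconsistency within SAP 4.3.3.1. Follow-up laboratory data are declared part of the analysis and ungraded tests are counted over the study period, but both grade tables stop at an undefined *during treatment*. If that phrase means On-Treatment, 1 of 4 scheduled post-baseline draws in every tier enters no grade table.

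The size is modest. The study is descriptive and safety is secondary. One draw in four is not one quarter of the risk, and no rate of first Grade 3–4 values at follow-up is available. The 11–14% residual rests on a half-life inferred from an example in the contraception criterion and on the SAP target days. A reader might work out about 18%, from 2^(−56/22.4) = 0.177. That requires a draw exactly 56 days after the last dose, as the protocol's description of the visit suggests, whereas the SAP targets fall 63–70 days after it.

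**What to change.** In SAP 4.3.3.1:

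1. Replace *during treatment* with the On-Treatment period as defined in SAP 6.2.1, and keep the worst-grade and ≥2-grade-shift tables on that period as the primary displays.
2. Repeat both tables for on-treatment plus the 8-week follow-up, including unscheduled draws. This follows the two-period layout that SAP 4.3.2 already uses for AEs.

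No new data are needed, only SAP wording and a second run of two existing table programs. The downside is a few more pages of output, and follow-up grades that are harder to attribute to the drug, which is why the on-treatment tables should stay primary.
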